N	Number (typically refers to participants)
NIH	National Institutes of Health
OHRP	Office for Human Research Protections
OHSR	Office of Human Subjects Research
PANAS- SF	Positive and Negative Affect Schedule
PI	Principal Investigator
QA	Quality Assurance
QC	Quality Control
SAE	Serious Adverse Event/Serious Adverse Experience
SMDDS	Symptoms of Major Depressive Disorder Scale
SOP	Standard Operating Procedure
tDCS	Transcranial direct current stimulation
US	United States
WRAT-4	Wide Range Achievement Test-4 Fourth Edition

CONFIDENTIAL

Protocol Summary

Title	A Pilot Study of the Immediate Effects of Single-Session DLPFC tDCS on Attention Bias in Depression
Short Title	Change in Depressive Attention Bias with DLPFC tDCS
Brief Summary	Depression and other psychiatric conditions are marked by exaggerated, preferential processing (or attention bias) of negative information relative to neutral or positive information. This depression-related attention bias can be measured using the Dot Probe task and Visual Search task, that allow assessment of the degree to which one shows bias toward negative information in the presence of neutral or positive information. A clinically effective treatment for depression is noninvasive brain stimulation with transcranial direct current stimulation (tDCS), targeting the dorsolateral prefrontal cortex (DLPFC), delivered in repeated sessions across a period of time. Here, we will test the effect of a single session of DLPFC tDCS on attention bias in individuals with mild to moderate depression. We predict that a single session DLPFC tDCS will alter depression-related, negative attention bias. Further, we compare this effect across the mild to moderate depression to healthy controls.
Objectives	To test if we can modify or reduce negative attention bias in depression following a single session of left anodal DLPFC tDCS.
Methodology	Prospective
Endpoint	Attention bias and subjective depressive symptoms (affect/mood) at before and after a single-session tDCS.
Study Duration	One year
Participant Duration	A single 2.5 hour research visit
Population	Female participants, ages of 18-45, with mild to moderate depression for depression group, no to minimal depression for healthy control groups.
Study Sites	[name] – NYU Dept. of Neurology
Number of participants	N=75 participants
Study Product	Transcranial direct current stimulation
Statistical Analysis	Pre-post tDCS comparison analyses using t-tests and correlations

CONFIDENTIAL

Schematic of Study Design

Pre-Screen	
• Eligibility pre-screen to determine general eligibility including BDI-II screen
Study Visit	
• Obtain Informed Consent• Mini International Neuropsychiatric Interview (MINI) (Screening)• Beck Depression Inventory (BDI-II) (Screening)• Beck Anxiety Inventory (BAI)• Hamilton Depression Rating Scale (HAM-D)• Symptoms of Major Depressive Disorder Scale (SMDDDS)• Healthy controls will complete a brief computer-based word puzzle task before the tDCS session, assigned to one of two conditions: difficult/unsolvable or easier
Pre-tDCS Administration	
• Positive and Negative Affect Schedule-SF (PANAS);• Analog Mood Scale (AMS)• Dot Probe Task (DP) and Visual Search (VS) Task
tDCS Administration	
• tDCS tolerability test• 30 minutes of tDCS (up to 2.0mA)
Post-tDCS Administration	
• PANAS• AMS• DP and VS Tasks

CONFIDENTIAL

Key Roles

Principal Investigator:

[name]
NYU Langone Health
Department of Neurology
[name]
[contact]
[contact]

Sub-Investigators:

[name]
NYU Langone Health
Department of Neurology
[name]
[contact]
[contact]

[name]
Department of Neurology, NYU Langone Health
[name]
[name]
[contact]
[contact]

1 Introduction, Background Information and Scientific Rationale

1.1 Background Information and Relevant Literature

Depression is characterized by distinct cognitive and emotional disruptions (Mathews & MacLeod, 2005; Winer & Salem, 2016), and the symptom burdens associated with the disease are tremendously debilitating to those who are affected (Lorenzo-Luaces, 2015). Depression is highly prevalent globally, and occurs twice as often in females than in males consistently in almost every part of the world (Culbertson, 1997; Nolen-Hoeksema & Hilt, 2009; Weissman & Klerman, 1977). Cognitive models of depression have shown depression-related attention bias (AB), a selective and exaggerated preferential processing toward negative information and stimuli, as a key mechanism in the etiology and maintenance of depression pathology (Bar-Haim et al., 2007; Mathews & Macleod, 1985, 2002; Peckham et al., 2010). Particularly, AB is presented as increased attention to negative, mood congruent stimuli and reduced attention to positive, mood-incongruent stimuli in depression (Trapp et al., 2018). Furthermore, this negative AB, which could be measured and quantified by various cognitive tasks such as the Dot Probe Task (Mathews & Macleod, 1985, 2002), has shown significant difference between depressed versus non-depressed individuals, indicating that negative AB is a robust measure of depression-related cognitive disruptions (Peckham et al., 2010). Other tasks such as the Visual Search (VS) Task (Wolfe & Horowitz, 2017), which is a task that measures facilitation and interference effects of attention that are disrupted in emotional and stress-related disorders, have shown robust findings in anxiety and PTSD (e.g., Pineles et al, 2009), but less is known about depression (Bodenschatz et al., 2021; Rinck & Becker, 2005). Importantly, negative AB was shown in clinical depression, non-clinical dysphoria, research subjects undergoing depressive mood induction, and in those who have recovered from depressive episodes (Joormann & Gotlib, 2007; Peckham et al., 2010; Trapp et al., 2018).

Noninvasive brain stimulation (NIBS) is an effective treatment for depression when applied in repeated sessions targeting the DLPFC. tDCS is one type of NIBS with a large body of clinical evidence supporting its PRIMSA Level A recommendation as “definitely effective” for the treatment of a major depressive episode (Fregni et al., 2021; Razza et al., 2020). In tDCS, low amplitude current is delivered through electrodes placed

CONFIDENTIAL

on the scalp to the target regions of interest. tDCS has been extensively demonstrated to be a safe and tolerable treatment, with no serious adverse events reported across clinical trials to date (Bikson et al., 2016).

In treatment of MDD, the use of tDCS is based on evidence of an interhemispheric functional asymmetry in depressive states that leads to a hypoactivation of the left dorsolateral prefrontal cortex (DLPFC) and hyperactivation of the right DLPFC (Grimm et al., 2008). The DLPFC is connected to the frontoparietal network (FPN), which has been found to be underactivated in depression (Korgaonkar et al., 2013). Most importantly, past studies suggest that the use of tDCS over the DLPFC may increase cognitive performance of people with depression, mainly due to the fact that DLPFC is involved in complex cognitive processes and attentional network (Brunoni & Vanderhasselt, 2014; Dedoncker et al., 2016). This further implies that application of tDCS in the DLPFC may also modulate attention associated with negative attention bias associated with depression, as well as potentially reducing depressive symptoms.

Recent studies have noted that a single session of DLPFC tDCS administration can reduce AB in patients with anxiety disorders (Heeren et al., 2017), but more research is needed to support the impact of short-term (i.e., single-session) tDCS in modifying or reducing AB, more specifically in depression.

In summary, tDCS has an extensive record of safety and tolerability. A large body of research has demonstrated its efficacy in reducing depressive symptoms following cumulative daily treatment sessions (e.g., 20 or more). While there is no clinical treatment benefit expected from a single session of tDCS, no study to date has yet to evaluate the immediate effect of single-session DLPFC tDCS in depression-related AB. This study will be one of the first studies to evaluate the efficacy of the single-session tDCS on depression-related attention bias and depressive mood and symptoms.

Rationale

We will test the effects of a single-session of DLPFC tDCS to alter negative attention bias in individuals with mild to moderate depression. In addition, for comparison, we will include healthy control participants 1:1 assigned to one of two pre-task conditions, where they will complete either difficult/unsolvable or easier computer-based word puzzles. The difficult/unsolvable condition will serve as a situational stressor. The easier word puzzle condition will provide neutral condition normative data. Findings will inform future studies and have the potential to inform the use of tDCS reducing symptoms of depression. Findings will inform future studies and have the potential to inform the use of tDCS reducing symptoms of depression.

2 Potential Risks & Benefits

2.1 Known Potential Risks

Risks associated with tDCS:

MINDD STIM (ybrain, South Korea) is medical-grade non-invasive brain stimulation system that uses weak electrical current to stimulate brain region of interest. MINDD STIM system has been used in over 33,200 sessions and 1,000 patients, without any serious adverse event reported. The side effects reported are similar to the ones reported (e.g., tingling, itching, warmth sensation) in other studies using other tDCS devices.

According to literature and the extensive experience of our lab (> 11,000 tDCS sessions delivered so far), there are no major risks associated with tDCS. Some people report tingling, itchiness and warmth sensation at the site of the electrodes. Rarely, the use of saline-soaked sponge electrodes can provoke skin dryness. tDCs do meet criteria for non-significant risk (Bikson et al., 2016). Additionally, there are no known serious adverse events associated with this type of stimulation. The current intensity for this study will be set at 2.0 mA. The safety and tolerability of tDCS current intensity at 2.0 mA has been assessed in multiple studies in which a single session of tDCS was found to be safe and well-tolerated.

For the reasons referenced above, tDCS meets the criteria for an abbreviated IDE (non-significant risk medical device):

CONFIDENTIAL

1. It is **not** intended as an implant and **does not** present a potential for serious risk to the health, safety, or welfare of a subject
2. It is **not** purported or represented to be for a use in supporting or sustaining human life and does **not** present a potential for serious risk to the health, safety, or welfare of a subject.
3. It is **not** for a use of substantial importance in diagnosing, curing, mitigating, or treating disease, or otherwise preventing impairment of human health and **does not** present a potential for serious risk to the health, safety, or welfare of a subject: the device will not be used for subject treatment and subjects standard medical treatment will continue regardless of their participation in the study
4. It **does not** otherwise present a potential for serious risk to the health, safety, or welfare of a subject.

Risks Associated with Mood Questionnaires: Completing questionnaires may produce some emotional distress in some participants. While we do not anticipate this to be a significant issue, participants will be allowed to take breaks as needed and may stop answering questions at any time without affecting their enrollment.

Risks Associated with Computer-Based Word Puzzle Task: If participants are assigned to the difficult/unsolvable condition, they may experience situational frustration or emotional discomfort. While we expect any discomfort to be brief and transitory, participants will be able to stop if the task at any point.

Risks Associated with Attention Bias Task: There are no anticipated risks from completing a computerized attention bias tasks.

Other risks:

There is minimal risk of breach of confidentiality. All data will be kept strictly confidential and stored in locked cabinets located at NYU Ambulatory Care Center (ACC), [name]. Electronic data will be stored on secure, password-protected, NYU Langone computers. Participants will be assigned a unique ID that will be used on all data collection instruments.

Unforeseeable risks: There may be risks associated with tDCS that are currently not known.

2.2 Known Potential Benefits

There is no direct expected benefit to the participants expected from the tDCS protocol as established. It is hoped that the knowledge gained from this study will help inform future research projects and ultimately help patients in the future.

3 Objectives and Purpose

3.1 Primary Objective

The researchers aim to test if a single-session tDCS targeting the DLPFC (left anodal) can modulate negative attention bias associated with depression and in comparison to healthy controls with and without experiencing a situational stressor.

3.2 Secondary Objective

Secondary objectives include evaluation of improvement in affect, reduction in depressive symptoms, and generation of primary data for future grant applications and basis of larger-sample studies.

4 Study Design and Endpoints

4.1 Description of Study Design

In this prospective pilot study we will recruit 25 female participants, ages 18-45 (inclusive), with mild to moderate depression (based on BDI-II score range 14-19 for mild and 20-28 for moderate) as well as 50 healthy control (defined by a BDI > 14) females of the same age range (18-45) to determine if a single-session of tDCS can alter negative attention bias. With the healthy control group, the recruited participants will be assigned to either

CONFIDENTIAL

the easy (n = 25) or difficult/unsolvable (n = 25) pre-tDCS word puzzle task condition. The group assignment will be pseudo-randomized (counterbalanced; e.g., alternating easy and difficult anagram conditions). The primary objective is to study if single-session tDCS will affect attention bias in depression and is not meant to treat depression. Subjects may or may not be receiving treatment for mild-moderate depression. If potential participant is severely depressed during the screening, standard clinical procedures will be used such as advising them to contact their treating physician and/or providing them a crisis hotline number (SAMHSA's National Helpline: [name], or to NYU Langone Psychiatry Associates at [contact].

For this initial pilot study, we are measuring subtle changes in response time latency at the millisecond level for attention bias. Because demographic factors of both age and sex are known to influence response times on attention tasks (Dykiert, Der, & Deary, 2012; Joormann & Gotlieb, 2007), we will limit the contribution of these factors in this initial pilot study.

The study will consist of a single 2.5 hour research visit that will take place at the NYU Ambulatory Care Center ([name]). After written informed consent is obtained (outlined in section 13.1), participants will have an eligibility screening which will include a semi structured interview (MINI). Eligible participants will complete depression and mood self-report questionnaires, two attention bias tasks (dot-probe and visual), and a single 30-minute tDCS session. Total study duration (including analysis, etc.) will be 1 year.

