5.5 Total Number of Participants and Sites

Recruitment will end when approximately 25 participants are enrolled for each condition (Total N = 75). It is expected that approximately 25 participants will be enrolled in order to produce 20 evaluable participants per each group (Total N = 60) for this pilot study.

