6.1 Pre-Screening

- Team member conducts phone pre-screening (including BDI-II) to determine general eligibility based on inclusion/exclusion criteria. Participants who meet the BDI-II criteria during the phone screen will not be required to repeat it if they schedule their visit within 2 days of the phone screen. Completing the BDI-II over the phone is a practical option that helps screen out those who are ineligible before

CONFIDENTIAL

they travel to clinic and it is suitable for phone use as participants can verbally rate the BDI-II statements on a scale from 0-4.

Those who score in the severely depressed range (29-63) will be offered to contact the NYU Langone Psychiatry Associates at [contact], or if outside the NY area the Substance Abuse and Mental Health Services Administration (SAMHSA) hotline at [name].

All data collected for the purposes of the eligibility pre-screening will be destroyed immediately if the potential subject is ineligible or does not sign an informed consent form at their baseline.

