6.2 Screening/Study Visit

- Obtain written informed consent (*25 minutes or however much time is needed*).
- Conduct eligibility screening/MINI/BDI-II (*15 minutes*)
- tDCS tolerability test (*2 minutes*)
- Administer depression surveys (BAI, HAM-D, and SMDDS) (*15 minutes*)
- Administer computerized attention bias dot-probe and visual search task (*30 minutes*)
- Administer pre-tDCS measures (PANAS and AMS; *10 minutes*)
- Complete tDCS session (*30 minutes*)
- Repeat PANAS and AMS (*10 minutes*)
- Repeat attention bias dot-probe task and visual search (*30 minutes*)

7 Study Procedures/Evaluations

After participants provide written informed consent, the following study procedures will take place during a single 2.5 hour research visit:

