7.4.2 Visual Search Task

In addition, the Visual Search task (e.g., Wolf & Horowitz, 2017) will be administered to further assess attention bias, particularly examining the interference and facilitation effects in attention using emotional stimuli (Rinck & Becker, 2005). The task uses emotional faces or words as stimuli, where the participant is instructed to search for the face that does not fit into the search set with respect to gender (i.e., the only male under three female faces, or the only female under three male faces), where the target and distractors are expressing different or same emotions (i.e., neutral-neutral, sad-neutral, happy-neutral, neutral-sad, neutral-happy, sad-sad, and happy-happy). Studies have shown that individuals with emotional and stress-related disorders show interference effect (i.e., emotional stimuli being the distractor) and facilitation effect (i.e., emotional stimulus being the search target), but less is known about depression (Bodenschatz et al., 2021; Rinck & Becker, 2005; Pineles et al., 2009). This study will use this task as an outcome measure of AB alongside the DP task. For this task, mean response time (the time between display onset and button press) to the target stimulus for each stimulus type is measured as the main outcome variable.

7.5 tDCS Session

tDCS Dose Selection and Tolerability: Participants will undergo a tolerability test to ensure tolerance of the stimulation intensity. In under 2 minutes, the tDCS device ramps up to the target stimulation of 2.0mA and ramps back down to 0mA. The tolerability test can be aborted at any time if the participant is uncomfortable. If 2.0mA stimulation is not tolerated, the participant will be given the option to proceed with a second tolerability test at a lower stimulation amperage (1.5 mA). Participants who cannot tolerate 1.5mA will be excluded as a screen failure.

tDCS settings: The MINDD STIM tDCS system is composed of a management component, treatment module, single-use sponge patches and supporting patches, a headband to hold in position the sponge patches, and 2 cables. A trained study technician will program the stimulation device through the management component setting to the following stimulation parameters:

- **Stimulation intensity:** 2.0 mA or 1.5 mA
- **Stimulation duration:** 30 minutes
- **Ramp up duration:** 30 seconds (beginning of stimulation)
- **Ramp down duration:** 30 seconds (end of stimulation)

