11.1 Study Hypotheses

A single-session tDCS to the left DLPFC will reduce negative attention bias in people with mild to moderate depression. There will be cohort differences across mildly depressed vs. healthy controls with easy anagram vs. healthy controls with difficult anagram (situational stressor) where the reduction of negative attention bias would be greatest in the depressed group compared to the healthy controls.

The primary objective of this study is exploratory data collection. These pilot study findings will be the necessary first step to inform future study design and hypotheses. We are collecting the healthy control pilot data to better interpret the pilot findings in patients with depression, and to provide us with expected ranges of change in our task measures. This inclusion of the anagram task is exploratory to inform future study designs. The use of the challenging anagram task is based from literature where the same paradigm has been used in healthy controls to study temporary states of negative affect (e.g., frustration, anxiety; Myruski et al., 2021).

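### The plan gives no random sequence, concealment or timing for assigning healthy controls to the easy or difficult anagram; under alternation, its only example, 49 of 50 assignments are foreseeable (minor)

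*Combined protocol and SAP*

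**What the plan says.** Section 4.1 plans 25 women with mild to moderate depression and 50 healthy controls, the controls divided 25 and 25 between an easy and a difficult or unsolvable word puzzle. On method it says only: "The group assignment will be pseudo-randomized (counterbalanced; e.g., alternating easy and difficult anagram conditions".

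The other descriptions add little:

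- The Rationale gives the ratio: "healthy control participants 1:1 assigned to one of two pre-task conditions".
- The Schematic of Study Design places the puzzle in the visit: "Healthy controls will complete a brief computer-based word puzzle task before the tDCS session".
- Section 7.3 repeats that half of the controls get each version.
- Section 5.5 sets the stopping point: "Recruitment will end when approximately 25 participants are enrolled for each condition".

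None of these describes how a sequence is generated, who holds it, whether staff can see the next assignment, or when a control is assigned. Section 11.3 uses the assignment in one place, an ANOVA over the three groups.

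**The concern.** A counterbalanced scheme fixes the group sizes but does not by itself make the next assignment unpredictable. Under strict alternation, anyone who knows one assignment knows all that follow.

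Staff have contact with candidates before the visit. Section 6.1 reads: "Team member conducts phone pre-screening (including BDI-II) to determine general eligibility". Eligibility is reviewed again in person (section 7.1), and one exclusion in section 5.2, on visual and motor ability, rests partly on staff judgement. The study has one site and describes no masking of staff to the puzzle condition. If assignment follows the pre-screen, a person deciding whether a control enters could know which puzzle that control would get.

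What is at stake is narrow. The two control arms are the only groups that the study itself assigns, so they are the only pair that randomisation could make comparable. If entry depended on the coming condition, an easy-versus-difficult difference could reflect who was enrolled and not only the stressor.

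**Working it through.** **Plan's own figures.** 50 controls at 1:1 give 25 and 25. Three groups of 25 give 75, and three of 20 evaluable give 60 (sections 5.5 and 11.2). These agree. The plan states no alpha, power, effect size or SD, so there is no power calculation to reproduce.

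**Foreseeability under alternation.** With n = 50, the assignments fixed once the first is known number n − 1 = 49, and 49/50 = 98%.

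**Comparison with random methods.** Take an observer who sees every past assignment and guesses the arm used less often so far, tossing a coin on ties. Only alternation comes from the plan; the other rows are for comparison.

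| Method | Expected correct guesses of 50 | Share |
|---|---|---|
| Strict alternation | 0.5 + 49 = 49.5 | 99% |
| Permuted blocks, random size 4 or 6 | 34.5 (40,000 simulated lists) | 69% |
| One random list, 25 and 25 | 25 + 2^49/C(50,25) − 0.5 = 28.95 | 58% |

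The block figure can be checked by hand. A block of size m gives m/2 + 2^(m−1)/C(m, m/2) − 0.5 correct guesses. For m = 4 this is 2 + 8/6 − 0.5 = 2.83 of 4 (71%). For m = 6 it is 3 + 32/20 − 0.5 = 4.1 of 6 (68%). The simulated 69% lies between them.

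The 98% and 99% for alternation differ because the first is the share known with certainty and the second adds half a correct guess for the opening assignment. All these figures measure predictability. None measures bias.

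**Balance under a 25/25 list.** If all 50 slots are filled, the split is exact. If recruitment stopped early, say at 40 controls (a hypothetical figure), the number in one arm is hypergeometric with SD √(40 × 0.5 × 0.5 × 10/49) = 1.43 and a 95% range of 17 to 23. The variance of the between-arm difference rises by n²/(4ab) = 40²/(4 × 17 × 23) = 1.023, or 2.3%, at the edge of that range. Blocks of 4 or 6 keep the assigned numbers within 3 of each other at any stopping point.

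**Where assignment falls in the visit.** Section 7.5 says of the stimulation tolerability test: "Participants who cannot tolerate 1.5mA will be excluded as a screen failure". The Schematic lists the word puzzle before that test. Section 6.2 lists the test before the depression surveys and leaves the puzzle out. On the Schematic's order, a control can be assigned, complete the puzzle, and then be removed as a screen failure. Section 7.1 deletes screen-failure data once recruitment ends, so removals by arm might leave no record.

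**The case against.** The strongest reply is that little depends on this. Section 11.1 calls the study's primary objective exploratory data collection and says of the puzzle: "This inclusion of the anagram task is exploratory to inform future study designs". Its directional hypothesis puts the greatest reduction in the depressed group, a comparison with controls that no allocation method could randomise. No section names easy versus difficult as a test of its own. The attention outcomes are timed within-person changes, so stable differences in speed largely cancel. Most control criteria are recorded facts or scores, which leaves little room for selection. The method is stated openly and is not presented as concealed randomisation.

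All of that stands, and it sets the weight of the point. It does not fill the gap: the primary objective in section 3.1 refers to controls with and without the stressor, the comparison enters the ANOVA, and the puzzle is there to guide later designs.

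A reader might infer more than the documents support:

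- **That the study uses alternation.** Section 4.1 offers it as an example and does not commit to it.
- **That staff know the condition when they screen.** This assumes that assignment follows the pre-screen; no section states the timing.
- **That the control comparison is biased.** Nothing shows that selection occurs, and nothing allows a bias to be sized.
- **That the main depressed-group result is compromised.** The paired test does not use this allocation.

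**Conclusion.** The point holds as a minor, cheaply remedied weakness. Confidence is high that sequence, concealment and timing are unspecified; no claim is made about an effect on results. The size, 49 of 50 assignments foreseeable, depends on alternation being followed and on staff knowing the previous assignment. The second condition is plausible at a single site with no masking described. The consequence is limited to how an easy-versus-difficult difference within the three-group ANOVA can be interpreted. N = 75 is unaffected.

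**What to change.** Replace the sentence on group assignment in section 4.1 with:

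> Healthy controls will be randomised 1:1 to the easy or difficult anagram from a computer-generated list (25 easy and 25 difficult, or permuted blocks of varying, undisclosed size). The list is prepared and held by a team member who does not screen or enrol participants and is not accessible to those who do. Each assignment is revealed only after consent and completed eligibility screening, immediately before the anagram.

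Two details need care. Section 13.4.1 gives the investigators and research coordinators access to study data and documents, so placing the list in the study database conceals it only if access is restricted. The sponsor should also reconcile the Schematic, section 6.2 and section 7.5 on the order of the tolerability test and the puzzle; this review takes no position on which order is right. If the reconciled text still allows removal after assignment, keep a de-identified count of removals by arm as an explicit exception to the deletion rule in section 7.1, and replace those controls within the list.

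The cost is one list, restricted access to it, and a short amendment; sample size, visits and analysis do not change. A 25/25 list delivers the stated 25 per arm when every slot is filled, with a small chance imbalance if recruitment stops early. Blocks hold closer balance but are more guessable (69% against 58%).
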